16 DESCRIPTIVE STATISTICAL ANALYSIS

16.1 PATIENT DISPOSITION

A summary of patients included in the study, as well as those who are non-evaluable and the reasons for this will be shown.

16.2 ENROLMENT VISIT

16.3 DEMOGRAPHIC DATA BY PATIENT

The categorical variables to be described are, N and (%):

- Number of implants by patient
- Gender (Male / Female)
- Medical conditions by patient (Yes / No):
 - Transient synovitis
 - Septic arthritis
 - Juvenile idiopathic arthritis
 - Cerebral palsy
 - Slipped Capital Femoral Epiphysis SCFE
 - Developmental Dysplasia of the Hip DDH
 - Blounts Disease
 - Neurogenic Hip Dysplasia
 - Ligamentary laxity
 - LeggCalvPerthes disease
 - Spina bifida
 - Down Syndrome
 - Chromosomal aberration
 - Other, specify (other medical conditions will be shown). The sponsor will give an elaboration of the open text with the correct number of other conditions inserted.
- Number of Medical conditions, considering other as one
- History of cardiovascular disease (Yes / No)
- History of diabetes (Yes / No)
- Family history of disease: Renal disease (Yes / No)
- Family history of disease: Deafness (Yes / No)
- Family history of disease: Cardiomyopathy (Yes / No)

- Family history of disease: Encephalopathy (Yes / No)
- Family history of disease: Diabetes Mellitus (Yes / No)
- Family history of disease: Hypertension Cardiovascular disease (Yes / No)
- Family history of disease: Thrombosis (Yes / No)
- Family history of disease: Malignancy (Yes / No)

16.4 DIAGNOSIS & X-RAY IMAGES BY PATIENT

The categorical variables to be described are, N and (%):

- The patient was treated for (Deformity Correction / Fracture)

16.5 DEMOGRAPHIC AND CLINICAL DATA BY IMPLANT

The descriptive statistic (Mean, SD, Median, Q₁, Q₃, Min, Max) will be shown for the following continuous variables:

- Age at surgery (calculated as date of surgery minus date of birth)
- Age at ICF signature (calculated as date of ICF signature minus date of birth)
- Height
- Weight
- BMI

The categorical variables to be described are, N and (%):

- Gender (Male / Female)
- Is this patient already included in this study for a previous JPS implantation? (Yes / No)

16.6 DIAGNOSIS & X-RAY IMAGES BY IMPLANT

The categorical variables to be described are, N and (%):

- The patient was treated for (Deformity Correction / Fracture). In case of fracture the following variables will be described:
 - The date of fracture is available?
 - Type of fracture (neck fracture / Pertochanteric fracture / Methaphyseal fracture / PathologicalImpending pathological fracture / Other (specify)).
- Treated bone (Distal Femur / Distal Tibia / Proximal Femur / Proximal Tibia)
- Body side (Left / Right)
- Body side (Only Left / Only Right / Both). A new variable will be generated based on original variable body side. For implants with only left, with only right and with both the variable "Treated bone (Distal Femur / Distal Tibia / Proximal Femur / Proximal Tibia)" will be described separately.
- Plane(s) of deformity: Frontal
- Plane(s) of deformity: Horizontal
- Plane(s) of deformity: Sagittal
- A new variable will be generated with the different combinations based on Plane(s) of deformity variables. (Frontal / Horizontal / Sagittal / Frontal-Horizontal / Frontal-Sagittal / Horizontal-Sagittal, etc...)
- Intended correction: Varus correction
- Intended correction: Valgus correction
- Intended correction: Rotational correction
- Intended correction: Shortening correction
- Intended correction: Extension correction
- A new variable will be generated with the different combinations based on Intended correction variables.

The descriptive statistic (Mean, SD, Median, Q₁, Q₃, Min, Max) will be shown for the following continuous variables:

- Degree Varus
- Degree Valgus
- Degree antecurvature

The categorical variables to be described are, N and (%):

- Was a software used during pre-planning ? (Yes / No)

- Did the patient refer pain at the affected limb before JPS application? (Not at all / A little bit / Moderately /Quite a bit /Extremely)
- In case of previous question is not equal to 'Not at all' VAS will be described
- In case of previous question is not equal to 'Not at all' VAS Pain Score according to the patient will be described
- Preoperative AP projection X-Ray
- Preoperative ML projection X-Ray

16.7 PRE-OP ROM AND WB BY IMPLANT

The categorical variables to be described are, N and (%):

- Pre operative Weight-bearing Grade (Non-weight-bearing (NWB) / Toe-touch weight-bearing (TTWB) / Partial weight-bearing (PWB) / Full weight-bearing (FWB))
- Which Range of Motion are available for this patient?
 - Knee Flexion
 - Knee Extension
 - Hip Flexion
 - Hip Extension
 - Hip Abduction
 - Hip Internal Rotation
 - Hip External Rotation
 - Ankle Joint Dorsiflexion
 - Ankle Joint Plantarflexion
 - None

The descriptive statistic (Mean, SD, Median, Q₁, Q₃, Min, Max) will be shown for the following continuous variables:

- ROM Knee Flexion
- ROM Knee Extension
- ROM Hip Flexion
- ROM Hip Extension
- ROM Hip Abduction
- ROM Hip Internal Rotation
- ROM Hip External Rotation
- ROM Ankle Joint Dorsiflexion
- ROM Ankle Joint Plantarflexion

17 SURGERY VISIT

17.1 DEVICE APPLICATION SURGERY

The descriptive statistic (Mean, SD, Median, Q₁, Q₃, Min, Max) will be shown for the following continuous variable:

- Duration surgery (hours)

The categorical variables to be described are, N and (%):

- How many plates were applied during this same surgery?
- Plate Size (3.0 mm / 3.5 mm / 5.0 mm)
- 3.0 mm Plate Type (Prox. Fem. 90° - 110° / Prox. Fem. 130°)
- 3.5 mm Plate Type (Prox. Fem. 90° / 120° / Prox. Fem. 130° / Prox. Fem. 140° / Prox. Fem. 150° / Wide Medial Tibia / Narrow Medial Tibia / Anterolateral Tibia / Distal Femur Plate 3.5 mm)
- 5.0 mm Plate Type (Prox. Fem. 90° / 120° / Prox. Fem. 130° / Prox. Fem. 140° / Prox. Fem. 150° / Distal Fem.)
- If '5.0 mm Plate Type' is equal to 'Prox. Fem. 90° / 120°': Plate holes number will be described
- If '3.5 mm Plate Type' is equal to 'Distal Femur Plate 3.5 mm': Plate holes number will be described
- If '5.0 mm Plate Type' is equal to 'Distal Fem.': Plate holes number will be described

The descriptive statistic (Mean, SD, Median, Q₁, Q₃, Min, Max) will be shown for the following continuous variable by the number of plates that were applied during this surgery:

- Duration surgery (hours)

Comparisons will be performed for this variable described above based on the number of plates using T-Student or U Mann Whitney, ANOVA or Kruskal Wallis, depending on the distribution of the variable.

The descriptive statistic (Mean, SD, Median, Q₁, Q₃, Min, Max) will be shown for the following continuous variable by MDD (Yes / No)¹ present in surgery visit:

- Duration surgery (hours)

Comparisons will be performed for this variable described above based on MDD at surgery using T-Student or U Mann Whitney depending on the distribution of the variable.

¹This variable will be obtained from Form MDD Description.

The descriptive statistic (Mean, SD, Median, Q₁, Q₃, Min, Max) will be shown for the following continuous variable by MDD (Yes / No)¹ present in surgery visit for each number of plates were applied during surgery separately:

- Duration surgery (hours)

Comparisons will be performed for this variable described above based on MDD at surgery using T-Student or U Mann Whitney depending on the distribution of the variable.

¹This variable will be obtained from Form MDD Description.

The categorical variable to be described is, N and (%):

- Did the patient receive a blood transfusion? (Yes / No)

The descriptive statistic (Mean, SD, Median, Q₁, Q₃, Min, Max) will be shown for the following continuous variables:

- If 'Did the patient receive a blood transfusion?' is equal to 'Yes': How many BT unit were used will be described

The categorical variables to be described are, N and (%):

- Number of Locking Screws used
- Number of Non-Locking Screws used
- Number of total screws as a sum of Number of Locking Screws+Number of Non-Locking Screws

The descriptive statistic (Mean, SD, Median, Q₁, Q₃, Min, Max) will be shown for the following continuous variables:

- Number of Locking Screws used
- Number of Non-Locking Screws used
- Number of total screws as a sum of Number of Locking Screws+Number of Non-Locking Screws

The descriptive statistic (Mean, SD, Median, Q₁, Q₃, Min, Max) will be shown for the following continuous variable:

- Radian dose

The categorical variables to be described are, N and (%):

- Post operative AP projection X-Ray
- Post operative ML projection X-Ray

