10.2 Description Event by Event

10.2.1 V0: Screening and Baseline

Prospective patients who meet the eligibility criteria will be enrolled in the study. Patients who agree to enter the study must sign the approved Informed Consent Form. Consented patients will have performed assessments as outlined in this protocol.

During the screening the investigator will evaluate the eligibility of the patients, checking all inclusion and exclusion criteria. Only those patients who meet all inclusion and exclusion criteria will be enrolled in the study. For each JPS implant a unique case number will be assigned (ID), and reported in the eCRF. Considering that each patient can contribute for more than one JPS implant: one patient can have more than one ID. In the eCRF the IDs are linked to the first ID assigned to the same patient by the clinical site. The patients not enrolled for non compliance will be considered as screening failures and will not be entered in the eCRF. Only for the enrolled patient, the Investigator will collect the demographic data and the medical history of the patient including information concerning the limb to be treated with JPS (baseline) such as the radiographic images and clinical examination.

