13 ANALYSIS POPULATION

The classification of the implants based on compliance with the screening criteria is defined below:

- **Evaluable implants** are defined as all implants who meet all inclusion criteria and none of the exclusion criteria described in the protocol.
- **Non-evaluable implants** are defined as all implants who fail to meet any of the inclusion criteria or meet any of the exclusion criteria.

The CRF contains the screening criteria information in the form of a binary variable (Yes/No) for each item described.

Analyses will be performed on evaluable implants.

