14 STATISTICAL ANALYSIS METHODS

The methods of analysis to be used for both objectives of the study and for description of the study variables are detailed below.

Quantitative variables will be described with measures of central tendency and dispersion: mean, median, SD (standard deviation), Q1 (first quartile) and Q3 (third quartile), minimum and maximum. Qualitative variables will be described using absolute and relative frequencies.

In the descriptive analysis of qualitative variables, two percentage columns will be presented, total percentage (%) and valid percentage (% valid), that are respectively, the percentage over the sum of valid responses plus missing values and the percentage over the total of valid responses.

For independent samples, parametric (t-test) or non-parametric (Mann-Whitney) statistical tests will be performed, depending on the distribution of the sample.

These tests will be used in all bilateral cases and with a level of significance of 0.048. In cases where a p-value less than 0.048 appears, it refers to the existence of statistical significance.

Clopper-Pearson confidence intervals will be shown at 95.2%.

Data will be analysed using SPSS v29.0.

An interim analysis, not planned at the start of the study, was performed after at least 20 subjects will be enrolled and completed the “Bone Consolidation” event.

The aim of this interim analysis was to verify the consistency of testing hypothesis and to confirm the historical data on the medical device safety and performance. Interim results were used to prepare the Clinical Evaluation Report (CER).

To preserve the integrity of the study results interpretation, a correction for multiplicity due to two planned analyses (interim+final) was implemented using the approach proposed by O'Brian-Fleming for sequential design (Shein –Chung Chow et Al Sample size calculations in Clinical Research 2003, Christopher Jennison et Al Group Sequential Methods with applications to clinical Trials,2000)

For this purpose, sample size was recalculated using this approach (all details are reported in the cited bibliography):

- The initial sample size was correct by factor 1.008 for a twosided test at 5% level and 80% power. The final sample size is $30 * 1.008 = 30.2$
- The probability level was corrected by factor 1.977, at interim the P value was 0.0052 while at the final analysis P value will be 0.048.

The corresponding confidence limits were at interim 99.5% and at final analysis 95.2%

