21.2 DEVICE REMOVAL SURGERY INFORMATION

The descriptive statistic (Mean, SD, Median, Q₁, Q₃, Min, Max) will be shown for the following continuous variable:

- Duration surgery

The descriptive statistic (Mean, SD, Median, Q₁, Q₃, Min, Max) will be shown for the following continuous variable by the number of plates were applied during device **application** surgery:

- Duration surgery (hours)

Comparisons will be performed for this variable described above based on the number of plates using T-Student or U Mann Whitney, ANOVA or Kruskal Wallis, depending on the distribution of the variable.

The descriptive statistic (Mean, SD, Median, Q₁, Q₃, Min, Max) will be shown for the following continuous variable by MDD (Yes / No)¹ present in device removal visit:

- Duration surgery (hours)

Comparisons will be performed for this variable described above based on MDD at surgery using T-Student or U Mann Whitney depending on the distribution of the variable.

¹This variable will be obtained from Form MDD Description.

The categorical variable to be described is, N and (%):

- Did the patient receive a blood transfusion? (Yes / No)

The descriptive statistic (Mean, SD, Median, Q₁, Q₃, Min, Max) will be shown for the following continuous variable:

- Radian dose

The categorical variables to be described are, N and (%):

- Post removal AP projection X-Ray
- Post removal ML projection X-Ray

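### The surgery-duration tests in SAP 17.1 and 21.2 name no unit but the implant, so records that share a patient, and possibly an operation, are tested as independent

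*SAP*

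**What the plan says.** SAP 13 classifies implants as evaluable or not and closes with "Analyses will be performed on evaluable implants". Protocol 10.2.1 gives each implant its own ID, lets one patient hold several, and links them to that patient's first ID.

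SAP 17.1 lists the item "How many plates were applied during this same surgery" beside plate-size and plate-type items. It then tests duration of the application surgery three ways: by number of plates ("Comparisons will be performed for this variable described above based on the number of plates using T-Student or U Mann Whitney", or ANOVA / Kruskal-Wallis), by presence of a device deficiency (MDD), and by MDD within each plate count. SAP 21.2 tests removal duration by MDD and "by the number of plates were applied during device" application.

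SAP 14 supplies the method, "For independent samples, parametric (t-test) or non-parametric (Mann-Whitney) statistical tests will be performed", two-sided at 0.048, and says a smaller p-value means statistical significance. Elsewhere the SAP states its unit: by patient in 16.3-16.4, by implant in 16.5-16.7, both in 23 and 24. Sections 17.1 and 21.2 state none and have no rule for records that share an operation or a patient.

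**The concern.** Operating time belongs to the operation, and operations belong to patients. The default unit is the implant. Two kinds of dependence follow.

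- **Shared patient.** Several IDs per patient are allowed, and SAP 16.5 collects "Is this patient already included in this study for a previous JPS implantation", but no test uses that flag.
- **Shared operation.** SAP 17.1 expects more than one plate in one operation. If each plate has its own ID and the whole operating time is stored under each ID, the same duration and plate count enter once per plate. Only the multi-plate groups are duplicated.

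In both cases the tests count more independent observations than exist. A chance difference in operating time would then be reported as significant more often than 4.8 %. The MDD comparison is the one a reader of a post-market safety report is most likely to notice.

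**Working it through.** **Inputs from the documents.** Two-sided level 0.048 from constant 1.977 (SAP 14); at most 40 implant cases (SAP 9); unit, IDs and tests as above. **Assumed, because the documents give no figures:** the mix of one- and multi-plate operations, MDD rate, operations per patient and intraclass correlation (ICC). Durations are simulated as normal with no true difference.

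**1. The plan's own level.** 2(1 − Φ(1.977)) = 0.0480. At the interim, 2(1 − Φ(1.977 × √2)) = 2(1 − Φ(2.796)) = 0.0052. Both reproduce.

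**2. Approximation for two groups.** Take n1 one-plate operations and n2 two-plate operations, each of the latter entered twice. The true variance of the mean difference is proportional to 1/n1 + 1/n2, but the test uses 1/n1 + 1/(2·n2). With R the ratio of the two, the rejection rate is about 2(1 − Φ(1.977/√R)).

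- 30/5: R = 0.2333/0.1333 = 1.75; 1.977/1.323 = 1.494; 13.5 %
- 20/10: R = 0.150/0.100 = 1.50; 1.977/1.225 = 1.614; 10.6 %
- 10/15: R = 0.1667/0.1333 = 1.25; 1.977/1.118 = 1.768; 7.7 %

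**3. Simulation, 40 records, 20,000 data sets, p < 0.048.**

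| One-/two-plate operations | t-test, duplicated | Mann-Whitney, duplicated | t-test, one record per operation | Mann-Whitney, one record per operation |
|---|---|---|---|---|
| 30/5 | 14.0 % | 14.2 % | 5.0 % | 4.4 % |
| 24/8 | 12.1 % | 11.5 % | 4.6 % | 4.6 % |
| 20/10 | 11.3 % | 11.1 % | 4.9 % | 4.5 % |
| 10/15 | 8.5 % | 8.0 % | 4.6 % | 4.0 % |

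Log-normal durations (sigma 0.4; 30/5, 20/10 and 10/15) give t-test 8.8-13.2 % and Mann-Whitney 8.1-14.0 % when duplicated.

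**4. Three groups (one, two, three plates), 10,000 data sets.** Mix 17/7/3: ANOVA 25.8 %, Kruskal-Wallis 25.4 %, against 4.8 % and 4.2 % with one record per operation. Mix 20/7/2: 26.4 % and 27.4 %, against 4.9 % and 3.3 %.

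**5. MDD yes/no, t-test.** The direction depends on how a deficiency is attached to the IDs.

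| Comparison | MDD on every ID of the operation | MDD on one ID only | One record per operation |
|---|---|---|---|
| All records, MDD rate 10-20 % | 7.5-14.2 % | 4.1-5.0 % | 4.6-4.9 % |
| Two-plate stratum, 8-15 operations, MDD rate 20-30 % | 18.2-20.6 % | 1.7-3.2 % | 4.6-4.9 % |

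In the stratum every operation is doubled, so R = 2 and the approximation gives 1.977/1.414 = 1.398, or 16.2 %. The simulated rate is higher because the t-test also credits degrees of freedom that do not exist.

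**6. Repeat patients, with one record per operation.** Take 15 patients with two operations each and the same plate count within patient. The variance is inflated by 1 + ICC. ICC 0.3: 1.977/√1.3 = 1.734, or 8.3 %. ICC 0.5: 1.977/√1.5 = 1.614, or 10.6 %. Simulation gives 8.5 % and 11.1-11.2 %. With 5 such patients and 20 with one operation, it gives 6.0 % and 7.2 %. One operation per patient, or the patient mean, gives 4.6-5.0 %.

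**The case against.** **The duplication depends on an unseen form.** This stands. No passage equates an implant with a plate, and the SAP 16.5 item on a previous implantation can be read as one record per implantation event. Protocol 9.2.2 bars other fixation plates on the same bone, which might imply several implants per multi-plate operation, but it may mean only plates of other systems. If one ID covers the operation, steps 2 to 5 do not apply. Step 6 does not need this assumption.

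**SAP 13 defines a population, not a unit for every table.** Partly right, since other sections set their own units. But 17.1 and 21.2 set none, which leaves SAP 13's sentence as the only instruction.

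**Two stronger readings are tempting, and the documents do not support them.**

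- A reader might infer from SAP 16.6, where a both-sides category is derived ("A new variable will be generated based on original variable body side"), that a bilateral case has two records. The same section builds combination variables from several items within one record, and its wording also fits an implant record marked with both sides. The passage is ambiguous and is not relied on.
- A reader might infer that the plate-count group in SAP 21.2 is already undefined. With one record per implant, each record has one application surgery and so one plate count. The question arises only once records are collapsed to one per removal.

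**The consequence is small.** This stands. Duration is in neither endpoint list, and Protocol 12.4 plans descriptive statistics.

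**Conclusion.** The point holds in a limited form. As written, SAP 13, 14, 17.1 and 21.2 allow records that are not independent into independent-sample tests. A shared patient follows from the documents; a shared operation is possible but unconfirmed.

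If every two-plate operation enters twice, the two-group plate-count test rejects in about 8-14 %, roughly two to three times the stated 4.8 %. That multiple applies only to the two-group plate-count test: the three-group test reaches about 25-27 %. The MDD test in the two-plate stratum reaches about 18-21 % if the deficiency is on both IDs, and is conservative at about 2-3 % if on one. Repeat patients alone give about 8-11 % in the heavier scenario and 6-7 % in the lighter one (ICC 0.3-0.5). All these rates rest on assumed mixes, MDD rates and ICCs.

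This is worth correcting but minor. No decision rule uses these p-values, and the primary endpoint, counted per patient, is unaffected.

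**What to change.** In SAP 17.1 and 21.2:

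1. State that surgery duration is described and compared with one record per operation, identified by patient and surgery date (in 21.2, patient and removal date). Count MDD as present if any deficiency occurred in that operation.
2. In 21.2, state how the plate count is set when one removal covers more than one application.
3. Because a patient may have several operations, use one operation per patient or a patient-clustered model, or label these p-values exploratory.

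If the eCRF already holds one duration record per operation, say so in place of item 1; item 3 is still needed.

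The cost is a few sentences and one programming step. IDs are already linked by patient and the SAP already uses both surgery dates, so no new data are needed. The downside is fewer records in the tests: in the 20/10 scenario, 20 + 2 × 10 = 40 records become 20 + 10 = 30.

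### SAP 17.1 tests surgery duration by device deficiency first without regard to number of plates and then in separate small strata, and never gives one plate-adjusted estimate

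*SAP*

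**What the plan says.** SAP 17.1 plans three sets of comparisons of the duration of the application surgery.

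1. By number of plates, with a two-group test, ANOVA or Kruskal-Wallis.
2. By MDD status with all cases together. The table is for the "continuous variable by MDD (Yes / No)¹ present in surgery visit", and the test is described as "based on MDD at surgery using T-Student or U Mann Whitney depending on the distribution of the variable".
3. By MDD status again, "present in surgery visit for each number of plates were applied during surgery separately", with the same choice of tests.

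SAP 14 fixes the level: "These tests will be used in all bilateral cases and with a level of significance of 0.048". It adds that a smaller p-value denotes statistical significance, so these are tests and not only tables. SAP 9 caps enrolment at 40 implant cases, and SAP 13 makes the implant the unit of analysis.

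The SAP gives no plate-adjusted or combined analysis, no minimum stratum size, no rule for a stratum with no MDD or one MDD, and no choice between exact and asymptotic p-values. SAP 21.2 plans a comparison of removal-surgery duration by MDD that is also unadjusted and has no stratified version. Protocol 12.4 describes the analysis as descriptive and rules out sub-group descriptive statistics because the sample is small.

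**The concern.** An operation with more plates may take longer and may also offer more opportunities for a deficiency. If both are true, the pooled comparison credits the MDD with time that belongs to the extra plates. The SAP treats plate number as a possible determinant of duration, since it tests that relation itself, yet it still plans a p-value that ignores it.

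The stratified tests deal with this by comparing like with like. The price is that a small number of MDDs is divided over cells of a study with at most 40 cases, and nothing puts the pieces back together. Some of those tests may be unable to reach significance under one of the two permitted methods, and the SAP does not warn of this. At stake is the answer to one question: by how much a deficiency prolongs surgery. The plan can return a biased pooled answer beside several weak separate ones.

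**Working it through.** **The level.** SAP 14 says: "The probability level was corrected by factor 1.977, at interim the P value was 0.0052", and 0.048 at the final analysis. With two equally spaced looks:
- final: 2 × (1 − Φ(1.977)) = 0.0480
- interim: 2 × (1 − Φ(1.977 × √2)) = 0.0052

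Both figures reproduce, so 0.048 is used below.

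**Floor of the exact Mann-Whitney test.** With m MDDs among n cases and no tied durations, the smallest two-sided p is 2 / C(n, m), reached when the groups separate completely.

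| MDDs in stratum | Largest n that fails | Smallest n that can reach p<0.048 |
|---|---|---|
| 1 | 2/41 = 0.0488 | 2/42 = 0.0476 |
| 2 | 2/C(9,2) = 2/36 = 0.056 | 2/C(10,2) = 2/45 = 0.044 |
| 3 | 2/C(7,3) = 2/35 = 0.057 | 2/C(8,3) = 2/56 = 0.036 |

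One MDD would need 42 cases in its stratum, above the cap of 40 for the whole study. No stratum of 7 or fewer can reach the level. With the asymptotic p-value (no continuity correction), one MDD never reaches it at any n (limit 0.083), two need n ≥ 8, and three or four need n ≥ 7.

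**The t-test.** There is no such floor. One MDD at 4.0 h against 2.0, 2.1 and 2.2 h: the mean difference is 1.9 h, the SD of the three is 0.1, the standard error is 0.1 × √(1 + 1/3) = 0.115, t = 16.5 on 2 degrees of freedom, p = 0.0037. The single MDD contributes nothing to the variance, so neither equal variance nor the shape of its distribution can be examined.

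**How often the floor would bite.** This depends on the MDD rate and the split by plates, neither of which is in the documents. The table shows the share of strata with both groups present that cannot reach 0.048 by exact Mann-Whitney, for 30 implants:

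| Assumed MDD rate | Split 16/10/4 | Split 20/10 |
|---|---|---|
| 3 % | 83 % | 79 % |
| 5 % | 77 % | 66 % |
| 10 % | 59 % | 42 % |
| 20 % | 40 % | 17 % |
| 30 % | 33 % | 7 % |

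**Size of a spurious pooled difference.** With no true MDD effect and two plate groups, it is d × [P(two plates given MDD) − P(two plates given no MDD)], where d is the extra time for two plates. Assume d = 1 h, 30 % two-plate operations, and MDD risk 10 % with one plate and 19 % with two:
- given MDD: 0.3 × 0.19 / (0.3 × 0.19 + 0.7 × 0.10) = 0.057/0.127 = 0.449
- given no MDD: 0.3 × 0.81 / (0.3 × 0.81 + 0.7 × 0.90) = 0.243/0.873 = 0.278
- difference: 0.17 h

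With risks of 5 % and 20 % it is 0.37 h. If either duration or MDD risk does not vary with plates, it is 0.

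**Simulation.** Assumptions, none from the documents: 36 operations; 60/30/10 % with 1/2/3 plates; 1.5 h plus 0.75 h per extra plate; normal errors with SD 0.5 h; MDD chance 5 to 20 % per plate; runs with fewer than two MDDs skipped (about 24 % of runs at the 5 % end).

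| Quantity | Result |
|---|---|
| No true effect: mean pooled difference | 0.22 to 0.26 h |
| No true effect: false positives, pooled t-test | 8 to 17 % |
| No true effect: false positives, plate-adjusted model | about 5 % |
| No true effect: any stratum t-test significant | 9 to 12 % |
| True 0.75 h effect: any stratum significant, exact Mann-Whitney | 27 to 78 % |
| True 0.75 h effect: any stratum significant, t-test | 53 to 87 % |
| True 0.75 h effect: one plate-adjusted test | 62 to 94 % |

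**The case against.** The strongest reply is that the SAP already does the sensible thing. It shows duration by plates, then by MDD, then by MDD within plate number, which is a crude analysis followed by a stratified one. The stratified step is a control for plates. This stands; what is missing is the combined estimate.

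Three stronger readings are tempting, and the documents do not support them.

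- *The pooled test is confounded.* That needs plate number to be related to both duration and MDD. The documents report neither relation, so the most that can be said is that the test is open to confounding.
- *The stratum tests cannot reach significance whatever the data.* That is true only in small or single-MDD strata, and only for Mann-Whitney. The SAP also permits the t-test, which can give a very small p-value with a single MDD. The defect there is an assumption that cannot be checked.
- *The planned analysis cannot answer the question.* In the simulation the stratum tests detect a 0.75 h effect in a fair share of runs. Set against t-tested strata, the power gain of the adjusted test is about 6 to 11 percentage points, much less than against Mann-Whitney. Any-stratum t-testing does pay for its power with 9 to 12 % false positives.

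Adjustment is also no cure when MDDs are very few. With one MDD in total, an exact van Elteren test has the same 2/n floor in that MDD's stratum, and a linear model rests on an equally uncheckable assumption. Finally, no endpoint or decision rule in the SAP uses this comparison.

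**Conclusion.** The point holds as a low-importance weakness in the choice of analysis. The pooled MDD test in SAP 17.1 ignores a factor that the SAP itself tests against duration. The stratified tests allow for that factor but give no combined estimate and have no minimum cell size.

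The floors for the exact Mann-Whitney test are arithmetic and need only the level of 0.048, the cap of 40 cases and untied durations. Everything else about size is conditional. The spurious difference of 0.22 to 0.26 h, the 8 to 17 % false positives and the power figures rest on the assumed plate split, durations and MDD rates. It would be wrong to conclude that most stratum tests are bound to fail: that is likely at low MDD rates or with three or more strata, but not with two larger strata and an MDD rate of 20 % or more.

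**What to change.** In SAP 17.1, replace the pooled and per-stratum MDD tests with one comparison of duration by MDD adjusted for number of plates. This can be a linear model of duration or log duration with MDD and number of plates as terms, or a van Elteren test stratified by number of plates. Report the adjusted difference with its confidence interval. Keep the tables by number of plates as description without p-values, and reconcile them with Protocol 12.4. Apply the same adjustment to the MDD comparison of removal-surgery duration in SAP 21.2. State that, if there are only one or two MDDs in total, the durations are described and no test is made.

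The cost is a change of SAP wording and one model in place of several tests, using data already collected. The downside is that a common MDD effect across numbers of plates is assumed; the descriptive tables let the reader judge whether that is reasonable.
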